7.2. Efficacy – Expansion cohort only

The antitumor activity of trabectedin given in combination with durvalumab will be evaluated as per RECIST v1.1, in terms of objective response under treatment, best overall response, 6-month objective response, 6-month progression-free status, , 1-year PFS and OS.

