7.2.2. Centralized Radiological Review (Institut Bergonié)

7.2.2.1. GENERAL PROCEDURE

Centralized radiological review will be performed to confirm disease status in comparison with baseline, Week#6, Week#12, Week#18, etc.... For patients included in the reference center, CT scan will be initially read by a radiologist who differs from the expert.

Review process will be centralized at Institut Bergonié and will be performed by a radiologist expert in soft tissue sarcomas. The judgment provided by the expert reviewer will be retained and used in statistical analyses.

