8. STUDY ENDPOINTS

8.1. Primary endpoint

Phase I / Dose escalation part

Primary objective of the phase I trial is to establish the recommended phase II dose (RP2D), the maximum tolerated dose (MTD) evaluated on the first cycle (D1 to D21), the safety profile, and the Dose Limiting Toxicities (DLT) of trabectedin given in combination with durvalumab.

Definition:

Dose-limiting toxicity (DLT):

A DLT is defined as an AE or laboratory abnormality that fulfills all the criteria below:

- Begins on the first 21 days of treatment.
- Is considered to be at least possibly related to the study treatment.
- Meets one of the criteria below, graded as outlined or according to NCI-CTCAEv4.03 :
 - Any grade-4 toxicity (except for vomiting without maximal symptomatic/prophylactic treatment and if toxicity is transaminitis, but which have to be resolved at Day 21, i.e. return to Baseline or grade 1).
 - Grade-3 non-haematological toxicity lasting > 7days (except for 1rst episode of nausea without maximal symptomatic/ prophylactic treatment and if toxicity is transaminitis, which have to be resolved at Day 21, i.e. return to Baseline or grade 1).
 - Grade-3 hematologic toxicity lasting for > 7days.
 - Grade 4 neutropenia with fever.
 - Grade > 2 thrombocytopenia with bleeding.

Endpoints:

- Toxicity graded using the common toxicity criteria from the NCI-CTCAE v4.03.
- Incidence rate of DLT at each dose level during the first 21 days.

Phase I / Expansion cohorts

Primary objective of the expansion cohorts is to evaluate preliminary signs of the antitumor activity of trabectedin given in combination with durvalumab in terms of objective response under treatment. Following RECIST v1.1 recommendations ([appendix 3](#)):

- Objective response rate (ORR) is defined as the proportion of patients with complete or partial response (CR, PR) as per RECIST v1.1 criteria.
- Objective response under treatment is recorded from study treatment initiation until the end of treatment and determined once all the data for the patient is known.
- Claimed responses will have to be confirmed at least 4 weeks later to ensure responses identified are not the result of measurement errors.
- **Disease status under treatment, whatever the response observed, will be centrally reviewed for all patients, by an independent expert radiologist. Reviewed data will be used for the efficacy analysis.**

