Conventional CT and MRI: This guideline has defined measurability of lesions on CT scan based on the assumption that CT slice thickness is 5 mm or less. If CT scans have slice thickness greater than 5 mm, the minimum size for a measurable lesion should be twice the slice thickness. MRI is also acceptable in certain situations (e.g. for body scans).

RESPONSE CRITERIA

Evaluation of Target Lesions

Complete Response (CR): Disappearance of all target lesions. Any pathological lymph nodes (whether target or non-target) must have reduction in short axis to <10 mm.

Partial Response (PR): At least a 30% decrease in the sum of the diameters of target lesions, taking as reference the baseline sum diameters.

Progressive Disease (PD): At least a 20% increase in the sum of the diameters of target lesions, taking as reference the smallest sum on study (this includes the baseline sum if that is the smallest on study). In addition to the relative increase of 20%, the sum must also demonstrate an absolute increase of at least 5 mm. (Note: the appearance of one or more new lesions is also considered progressions).

Stable Disease (SD): Neither sufficient shrinkage to qualify for PR nor sufficient increase to qualify for PD, taking as reference the smallest sum diameters while on study

Evaluation of Non-Target Lesions

Complete Response (CR): Disappearance of all non-target lesions and normalization of tumor marker level. All lymph nodes must be non-pathological in size (<10 mm short axis)

Note: If tumor markers are initially above the upper normal limit, they must normalize for a patient to be considered in complete clinical response.

Non-CR/Non-PD: Persistence of one or more non-target lesion(s) and/or maintenance of tumor marker level above the normal limits

Progressive Disease (PD): Appearance of one or more new lesions and/or unequivocal progression of existing non-target lesions.

Although a clear progression of "non-target" lesions only is exceptional, the opinion of the treating physician should prevail in such circumstances, and the progression status should be confirmed at a later time by the review panel (or Principal Investigator).

Definition of the Best Response

The best response determination in trial where confirmation of complete or partial response is required:

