3.2.2 Expansion cohorts

- Analyses will be conducted separately for sarcoma and ovarian cancer patients.
- Primary efficacy endpoint will be analysed based on the eligible and assessable population:
 - Each patient will be assigned one of the following categories:
 - Complete response
 - Partial response
 - Stable disease
 - Progression
 - Inevaluable for response
 - The rate of objective response (complete or partial response) under treatment will be reported:
 - All eligible and assessable patients will be included in the denominator for the calculation of the objective response rate (ORR).
 - The 95% two-sided confidence limits will be provided for the ORR (binomial law).
 - First endpoint conclusions will be based on the objective response rate ORR for all eligible and assessable patients (section 10.2) after centralized radiological review of the data.
- As regards to the other efficacy endpoints, the analyses will be carried out in the eligible and assessable population:
 - Each patient will be assigned one of the following categories:
 - Complete response
 - Partial response
 - Stable disease
 - Progression
 - Inevaluable for response
 - The rate of best overall response will be calculated as the number of patients alive with the best response (recorded from the start of the treatment) divided by the number of patients eligible and assessable.
 - The 6-month progression-free rate will be calculated as the number of patients remaining alive and progression-free at 6 months from the start of the treatment divided by the number of patients eligible and assessable.
 - The 6-month objective response rate will be calculated as the number of patients alive with complete or partial response at 6 months divided by the number of patients eligible and assessable.
 - The 95% two-sided confidence limits will be provided for the calculated rates (binomial law)
- The safety analysis will be performed on the safety population.
- Quantitative variables will be described using mean and standard deviations if the normality assumption is satisfied, else other descriptive statistics (median, range, quartiles) will be reported.
- Qualitative variables will be described using frequency, percentage and 95% confidence interval (binomial law).
- Survival endpoints will be analysed using the Kaplan-Meier method. The median survival rates will be reported with a 95% confidence interval. Median follow-up will be calculated using the reverse Kaplan-Meier method.

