3.2.4 Secondary endpoints

For dose escalation part: Only the patients assessable for safety (TOL = 1) will take part into this analysis.

For expansion cohorts: Only the patients evaluable for efficacy (ELI_EFF = 1) will take part into this analysis.

Criteria	eFORM variable	Control
Objective response rate, defined as the rate of complete or partial response according to RECIST v1.1	
ASSE_CYC (TUMOR ASSESSMENT) DT_MEASC (date of measurement) ME1RTLC-ME5 RTLC (measures of lesions) SUM_RTLC (largest diameters) EVA1RLNMC-EVA5 RLNMC (non-measurable lesions eval) RES_RTLC, RES_RNTL (target and non-target lesions) OV_REV (overall response) CR=1, PR=2, SD=3, PD=4, NE=5 New variables : NB_BORR (nb of objective response case)
 
END OF STUDY (END_STU) DT_EOS (date of end of study)
	Status at each TUMOR ASSESSMENT
6-month objective response rate , defined as the rate of complete or partial response at 6 months according to RECIST v1.1	
ASSE_CYC (TUMOR ASSESSMENT) DT_MEASC (date of measurement) ME1RTLC-ME5 RTLC (measures of lesions) SUM_RTLC (largest diameters) EVA1RLNMC-EVA5 RLNMC (non-measurable lesions eval) RES_RTLC, RES_RNTL (target and non-target lesions) OV_REV (overall response) CR=1, PR=2 TREATMENT DT1_START ((Day 1 of treatment)) New variables : NB_ORR (nb of objective response case at 6months)
	DT_START filled in ME1RTLC-ME5 RTLC (filled in if needed) SUM_RTLC C filled in and check recist1.1 criteria EVA1RLNMC-EVA5 RLNMC (filled in if needed) RES_RTLC, RES_RNTL (filled in) Compute number of patients with OV_REV in (1 or 2) at 6 months
6-month Non-progression rate (NPR) defined as the percentage of patients with CR, PR or stable disease (SD) according to RECIST v1.1, (CR, PR or SD more than 24 weeks)	
ASSE_CYC (TUMOR ASSESSMENT) DT_MEASC (date of measurement) ME1RTLC-ME5 RTLC (measures of lesions) SUM_RTLC (largest diameters) EVA1RLNMC_EVA5RLNMC (non-
	DT_START filled in ME1RTLC-ME5 RTLC (filled in if needed) SUM_RTLC C filled in and check recist1.1 criteria EVA1RLNMC-EVA5 RLNMC (filled

	
measurable lesions eval) RES_RTL, RES_RNTL (target and non-target lesions) OV_RESP (overall response) CR=1, PR=2, SD=3 TREATMENT DT1_START ((Day 1 of treatment)) New variables : NB_NPR (nb of non-progression case at 6 months)
	
in if needed) RES_RTL, RES_RNTL (filled in) Compute number of patients with OV_REV in (1 2 3) at 6 month for at least 24 weeks

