1 and 2-year Progression-Free Survival (PFS) defined as the time from study treatment initiation to the first occurrence of disease progression or death (of any cause), whichever occurs first.	
END OF TREATMENT FORM DT_SOT (Date of start of treatment) EOTSTATU (Status) EOTREAO (Reason end) DT_PROG (Date of progression if occurred) Type of progression (if progression occurred) FOLLOW UP FORM DT_FUP (date of visit) STATUSP (Vital status) PRO_LAS, DT_FPROG (date of progression) END OF STUDY (END_STU) DT_EOS (date of end of study) REA_STUD (reason) DT_DEATH (date of death)
	
Check if everything is filled in If (DT_PROG is blank) then Do; If (PRO_LAS=0) then { PFS= DT_EOS-DT_SOT ; If (REA_STUD='death') then IND_PFS=1 Else IND_PFS=0 } Else { PFS=DT_FPROG – DT_SOT; IND_PFS=1} End; Else { PFS= DT_PROG – DT_SOT; IND_PFS=1}

1 year Overall Survival (OS), OS is defined as the time from study treatment initiation to death (of any cause).	
END OF TREATMENT (EOTF) DT_SOT (start date of treatment) EOTSTAU (Status) EOTREAO (Reason end) FOLLOW UP FORM DT_FUP (date of visit) STATUSP (Vital status) END OF STUDY (END_STU) DT_EOS (date of end of study) REA_STUD (reason) DT_DEATH (date of death) DT_LFUP (date of last follow_up)
	
Check if everything is filled in If (STATUSP NE 'dead') then do; if (REA_STUD ='death') then { OS= DT_DEATH-DT_SOT; IND_OS=1; } Else {OS= DT_EOS-DT_SOT; IND_OS=0; } end; Else { OS= DT_LFUP -DT_SOT; IND_OS=1; }

Pharmacodynamic (PD) and predictive biomarkers analysis (levels of angiogenic and immunologic biomarkers in blood at baseline and different study time points).	
LABORATORY TEST BIOMARKERS AND CIRCULATING DNA
	

4 Annexes

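### SAP 3.2.4 dates PFS progression from the End of Treatment and Follow-up forms with no centrally read variable, although the protocol has the expert reader's judgement used in the analyses

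*SAP*

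**What the plan says.** **Protocol.** Section 7.2 opens: "The antitumor activity of trabectedin given in combination with durvalumab will be evaluated as per RECIST v1.1, in terms of objective response under treatment", and the same sentence goes on to best response, the 6-month measures, 1-year PFS and OS. Beneath it, 7.2.2.1 has an expert radiologist confirm disease status at weeks 6, 12, 18 and onward, and adds: "The judgment provided by the expert reviewer will be retained and used in statistical analyses". Section 8.1, under the primary ORR endpoint and speaking of status under treatment, says: "Reviewed data will be used for the efficacy analysis".

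**SAP, response.** Section 3.2.2 bases the primary ORR conclusion on the rate "after centralized radiological review of the data". It has no matching sentence for PFS or the 6-month rates.

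**SAP, programs in 3.2.4.** PFS progression comes from "DT_PROG (Date of progression if occurred" on the End of Treatment form. If that is blank, it comes from "PRO_LAS, DT_FPROG (date of progression" on the Follow-up form, and otherwise from end-of-study data. The 6-month ORR is counted from OV_REV on the tumour assessment form. The 6-month non-progression row lists "OV_RESP (overall response" in its variable column, but its program counts OV_REV.

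**Protocol Appendix 3.** For progression confined to non-target lesions, which it calls exceptional, "the opinion of the treating physician should prevail in such circumstances", with later confirmation by the review panel or the Principal Investigator.

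**The concern.** This is an open-label trial without a control arm, and central reading is the protocol's safeguard against assessor bias in imaging endpoints. A reader of the protocol would expect reported PFS to rest on it. If the SAP is followed as written, PFS rests on dates from two forms that have no stated link to the central reading.

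The plan also reports the 6-month landmark twice, from different variables: as a non-progression proportion in Table 8.2 and as a PFS rate in Table 9.1. With cohorts this small, one patient classed differently is visible in the results, and the SAP has no rule for reconciling the two.

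**Working it through.** **Which source feeds which result**

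| Result | Variable programmed | Form | Reader stated? |
|---|---|---|---|
| Primary ORR conclusion | OV_REV listed (3.2.3) | Tumour assessment | Central, by the text of 3.2.2 |
| 6-month ORR | OV_REV | Tumour assessment | No |
| 6-month non-progression | OV_REV programmed, OV_RESP listed | Tumour assessment | No |
| PFS (median, 6-month, 1-year) | DT_PROG, then DT_FPROG, then end-of-study data | End of Treatment, Follow-up, End of Study | No |

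**Are the PFS dates site dates?** The SAP does not say so directly. Three facts point that way:
- Protocol 11.2.1 restricts data entry to investigators and their research assistants.
- The tumour response listing (SAP 4.2.4) has a central-review field.
- The end-of-treatment listing (SAP 4.2.5), which carries the date and type of progression, has none.

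**Does it matter which reader OV_REV represents?** The plan needs correcting either way:
- If OV_REV is the central reading, the 6-month rates are central and PFS is not.
- If OV_REV is the site reading, the variable listed for ORR in 3.2.3 is not the one that the text of 3.2.2 calls for, and the variable table must be brought into line with that text.

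**Same landmark, same population.** Tables 8.2 and 9.1 both cover patients eligible and assessable for efficacy. Some numerical difference is expected, because one is a crude proportion and the other a Kaplan-Meier estimate. The problem is that a patient's status at 6 months can itself differ between them.

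**Size.** The denominator is the plan's own figure (Protocol 9.1). A Gehan first stage needs the smallest n with (1 − 0.20)^n ≤ 0.05. Since 0.8^13 = 0.0550 and 0.8^14 = 0.0440, n = 14, as stated.
- One discordant patient: 1/14 = 7.1 points on a crude rate.
- Two in the same direction: 2/14 = 14.3 points.
- Illustration with assumed counts and exact 95% limits: 5/14 = 35.7% (12.8 to 64.9) becomes 4/14 = 28.6% (8.4 to 58.1) or 6/14 = 42.9% (17.7 to 71.1).
- Number affected: the documents give no local/central discordance rate. At an assumed 10% to 30%, 0.10 × 14 = 1.4 to 0.30 × 14 = 4.2 patients per cohort.

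The 7.1 points apply to a crude proportion. They are not a ceiling for a Kaplan-Meier rate, where a step taken after censoring can exceed 1/14.

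**The case against.** **Different assessors.** It is tempting to conclude that PFS and the 6-month rates come from different assessors. The documents do not establish this. OV_REV sounds like a reviewed response but is labelled only as overall response, and the non-progression row names two variables. What is shown is different data sources with unstated readers.

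**Type of progression.** This field might be read as proof that DT_PROG includes clinical, non-radiological progression. The SAP never defines it, and it could equally distinguish local from metastatic disease.

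**Appendix 3.** One might say this rule causes the split between PFS and the 6-month rates. It cannot: a rule on how progression is called would affect both. It is also confined to an exceptional case and asks for later confirmation. What remains is a conflict with 7.2.2.1 over whose reading counts, since confirmation by the Principal Investigator would not be a central reading.

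**Scope of central review.** The sentence in 8.1 concerns status under treatment and sits under ORR. Section 7.2.2.1 is broader, but review of scans taken after treatment ends, the setting of DT_FPROG, is not clearly promised. This stands, and it limits any remedy that relies only on central PD.

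**Consequence.** PFS is secondary, all analyses are descriptive, and the rule for further testing uses objective response alone. This also stands, and it keeps the point away from the trial's main conclusion.

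**Conclusion.** The point holds in limited form. For the expansion cohorts, the protocol has the expert's judgement used in the analyses and counts 1-year PFS as efficacy, while the SAP program builds PFS from End of Treatment and Follow-up dates with no centrally read input. The reader behind the 6-month rates is undefined, and the non-progression row contradicts itself on the variable. Tables 8.2 and 9.1 can therefore class the same patient differently, at 7.1 points on a crude rate per patient among 14.

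This rests on reading DT_PROG and DT_FPROG as site entries, which follows from the forms and the data-entry rule and is not stated outright. How many patients would be affected cannot be known from the documents. A reader might infer that the ORR result is compromised too; it is not, because SAP 3.2.2 ties that conclusion to central review. The SAP should be corrected before PFS is analysed.

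**What to change.** In SAP 3.2.4:
1. State the reader of OV_REV and of OV_RESP. Use the centrally reviewed variable for ORR, best response and both 6-month rates, and correct the non-progression row to match.
2. Set the PFS progression date to DT_MEASC of the first assessment read centrally as PD. Keep death from any cause as an event.
3. Where there is no post-baseline scan, or progression is found after treatment ends and is not centrally read, keep DT_PROG or DT_FPROG as the event date and flag the case. SAP 2.4 retains in the efficacy population patients who progress before any post-baseline assessment, and Protocol 4.4 has 12-weekly follow-up for those who stop without progression. A rule based only on central PD would censor the first group unless they died and could lose events in the second, biasing PFS upward.
4. Report PFS from DT_PROG/DT_FPROG for all patients as a labelled investigator sensitivity analysis.

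In the protocol, reconcile the Appendix 3 sentence on non-target progression with 7.2.2.1 for the purpose of analysis only; this does not touch treatment decisions.

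The cost is SAP text, programming and one reconciled sentence. On-treatment tumour evaluations are already sent for review under Protocol 7.2.2. The drawback is that local PD not confirmed centrally becomes censored, possibly informatively, because such patients may stop treatment and scanning. That is why both analyses should be shown together.

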4.4. Definitions of duration of Study and Treatment (Per Patient)

Patients will receive study treatment as long as it is considered to be in their best interest. Patients will be evaluated at scheduled visits in up to three study periods:

- **Pre-treatment (PRE TT):** from signature of informed consent to the first administration of study drugs.
- **Treatment (TT):** from the first administration of study drugs to treatment discontinuation.
- **Follow-up (FUP):** after treatment discontinuation, patients will be followed up four weeks later for toxicities, and beyond if grade 3 or 4 toxicity, until resolution.

Patients who discontinue treatment *without progression* will be **followed every 12 weeks** until:

1. Disease progression,
2. Initiation of other antitumor therapy,
3. Death, or
4. The date of study termination, whichever occurs first.

After documented progression or start of a new antitumor therapy, patients will be **followed every 6 months until:**

1. Death, or
2. The date of study termination, whichever occurs first.

Patients will be considered to be **on-study** from the signature of the informed consent to the end of follow-up period.

Patients will be considered to be **on-treatment** for the duration of their treatment until 30 days (4 weeks) after the last treatment administration, except if the patient starts a new antitumor therapy before this period.

Patients may withdraw their consent at any time; no further study activities will be conducted on them.

Treatment discontinuation occurs when an enrolled patient ceases to receive the study medication or starts a new antitumor therapy, regardless of the circumstances, and is defined as 30 days after the day of the last treatment administration, unless the patient starts a new antitumor therapy, in which case the date of administration of this new antitumor therapy will be considered the date of treatment discontinuation. The primary reason for any discontinuation will be recorded on the patient's case report form (CRF). If a patient discontinues treatment, every effort should be made to complete the scheduled assessments. Administration of the study treatments should be permanently discontinued if this is considered to be in the best interest of the patient. More specifically, treatment will be discontinued due to any of the following reasons:

- Withdrawal of consent or lost to follow-up,
- Disease progression,

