- Adverse event that, in the opinion of the investigator or the sponsor, contraindicates further dosing,
- Subject is determined to have met one or more of the exclusion criteria for study participation at study entry and continuing investigational therapy might constitute a safety risk,
- Pregnancy or intent to become pregnant,
- Grade ≥ 3 infusion reaction,
- Initiation of alternative anticancer therapy including another investigational agent,
- Intercurrent illness of sufficient magnitude to preclude safe continuation of the study,
- Patient refusal and/or non compliance with study requirements,
- Protocol deviation with an effect on the risk/benefit ratio of the clinical trial

Patients still experiencing a non-progression after 6 cycles will then be able to continue treatment off-study at the discretion of the investigator.

Study discontinuation occurs when an enrolled patient ceases to participate in the study, regardless of the reason (as detailed under "Follow-up" in Section 3.2.8). Patients have the right to withdraw consent at any time; if this is the case, no further follow-up should be performed.

The date and reason for study discontinuation will be clearly documented on the patient's CRF.

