8.2. Secondary endpoints

Phase I / Dose escalation part

- Preliminary signs of antitumor activity in terms of:
 - Best overall response is defined as the best response recorded from the start of the study treatment until the end of treatment taking into account any requirement for confirmation as per RECIST v1.1 criteria ([appendix 3](#)):
Following RECIST v1.1 recommendations:
 - The best overall response is determined once all the data for the patient is known.
 - Claimed responses will have to be confirmed at least 4 weeks later to ensure responses identified are not the result of measurement errors.
 - Objective response rate (ORR) is defined as the proportion of patients with complete response or partial response according to RECIST v1.1 criteria ([appendix 3](#)). ORR under treatment and 6-month ORR will be reported. ORR under treatment is recorded from study treatment initiation until the end of treatment. Following RECIST v1.1 recommendations:
 - ORR under treatment is determined once all the data for the patient is known.
 - Claimed responses will have to be confirmed at least 4 weeks later to ensure responses identified are not the result of measurement errors.
 - Progression-free rate (PFR) is defined as the proportion of patients with complete response, partial response or stable disease more than 24 weeks as defined as per RECIST v1.1 criteria ([appendix 3](#)). 6-month PFR will be reported. . Following RECIST v1.1 recommendations, claimed responses will have to be confirmed at least 4 weeks later to ensure responses identified are not the result of measurement errors.
 - Progression-free survival (PFS) is defined as the time from study treatment initiation to the first occurrence of disease progression or death (of any cause), whichever occurs first. 1-year PFS rate will be reported.
 - Overall Survival (OS) is defined as the time from study treatment initiation to death (of any cause). 1-year OS rate will be reported.
- Pharmacodynamic study:
 - Blood samples:
 - Serum level of cytokines, kynurenine and immunophenotyping of circulating immune cells
 - Analyses of circulating DNA for identification and monitoring of mutations observed at the level of the circulating tumor cells (liquid biopsies concept).
 - Tumor samples: Fresh pre-treatment and on-treatment tumor biopsies will be performed. Samples will be formalin fixed and paraffin-embedded or fresh frozen, and will be analyzed for:
 - Hematoxylin and eosin staining (H&E).

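### The SAP's PFS and OS programs do not reliably compute the definitions beside them: death dates, one blank-field case and the PFS censoring date need correcting

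*SAP*

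**What the plan says.** Protocol 8.2 defines PFS as time from treatment start to first progression or death from any cause. For OS it says: "Overall Survival (OS) is defined as the time from study treatment initiation to death (of any cause"). SAP 3.2.4 repeats both definitions and sets a program beside each.

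**PFS program.**
- If DT_PROG (end-of-treatment form) is filled, PFS runs to that date and is an event.
- If DT_PROG is blank and PRO_LAS is 0: "If (PRO_LAS=0) then { PFS= DT_EOS-DT_SOT". This is an event if the reason for leaving the study is death, and otherwise censored.
- If DT_PROG is blank and PRO_LAS is anything else: "Else { PFS=DT_FPROG – DT_SOT; IND_PFS=1".

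DT_DEATH and STATUSP are listed as inputs, but the code uses neither.

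**OS program.**
- If STATUSP is dead: "Else { OS= DT_LFUP -DT_SOT; IND_OS=1". The date field is labelled "DT_LFUP (date of last follow_up").
- Otherwise, if REA_STUD is death, the time runs to DT_DEATH and is an event.
- Otherwise the patient is censored at DT_EOS.

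Both programs open with a check that all fields are completed. No action is stated for a field that is blank, and SAP 3.1 says missing data are not imputed. Neither document states a PFS censoring rule in words.

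Under Protocol 4.4 a patient is on study "from the signature of the informed consent to the end of follow-up period". "After documented progression or start of a new antitumor therapy, patients will be" seen every 6 months; before that, patients who stop treatment without progression are seen every 12 weeks.

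**The concern.** Time to death should end on the date of death, and the same death should carry the same date and status in both endpoints. The programs guarantee neither. Each can substitute an administrative date for a death date that is listed among its own inputs, so a patient's PFS can exceed his or her OS, which the definitions rule out.

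One ordinary situation may also return no PFS time at all: a death on treatment without progression. PRO_LAS sits on the follow-up form, and such a patient may never have one.

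Censoring at end of study credits as progression-free any time on study in which nobody looked for progression. Protocol Appendix 3 says the analysis plan must deal with missing assessments when progression is determined, and the SAP does not.

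At stake are the median, 6-month and 1-year PFS and OS figures in SAP 4.3.9 and 4.3.10.

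**Working it through.** The plan gives no figure to reproduce. The check applies the program rules to constructed patients and then scales the effect.

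**Inputs.** Program rules: SAP 3.2.4. Definitions: Protocol 8.2. Assessable patients per expansion cohort: 14 (Protocol 9.1.1, expansion cohorts). All patient dates below are invented, in days from treatment start. A blank does not equal 0, and a difference involving a blank date is missing.

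**Step 1. Rules applied literally (DT_PROG blank throughout).**

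| Patient | Program PFS | Program OS | By definition |
|---|---|---|---|
| A. Died 300; REA_STUD death; DT_EOS 300; STATUSP not dead; PRO_LAS 0 | 300 event | 300 event | both 300: correct |
| B. As A, but DT_EOS 380 | 380 event | 300 event | both 300; PFS exceeds OS |
| C. As A, but STATUSP dead and DT_LFUP 200 | 300 event | 200 event | both 300; OS too early |
| D. Died on treatment, day 60; no follow-up form, so PRO_LAS and DT_FPROG blank | missing, IND_PFS=1 | 60 event | both 60 |
| E. PRO_LAS blank, DT_FPROG 150; alive at DT_EOS 365 | 150 event | 365 censored | correct |
| F. Died 300; STATUSP dead; REA_STUD not death; DT_EOS and DT_LFUP 380 | 380 censored | 380 event | both 300 event |
| G. Alive, no progression, last scan 120, DT_EOS 365, PRO_LAS 0 | 365 censored | 365 censored | PFS unobserved after 120 |

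A and B show that the PFS dating error depends entirely on what DT_EOS holds. B and C show that dating errors can run late or early. D and E show that a blank PRO_LAS loses the PFS time only when DT_FPROG (and DT_PROG) is blank too. F requires two forms that disagree.

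**Step 2. Scale in a cohort of 14.** Every line starts at zero.

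*Dating of deaths.* One death moved across day 365 is 1/14 = 7.1 points. For an average effect, assume exponential survival with true 1-year OS S, and a fraction p of deaths dated g days late:

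shift = p × (S^((365−g)/365) − S)

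| | S = 0.3 | S = 0.5 | S = 0.7 |
|---|---|---|---|
| g = 14, p = 1 | +1.4 | +1.3 | +1.0 |
| g = 14, p = 0.25 | +0.4 | +0.3 | +0.2 |
| g = 42, p = 1 | +4.5 | +4.2 | +2.9 |
| g = 42, p = 0.25 | +1.1 | +1.0 | +0.7 |

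If the recorded date falls before death, the sign reverses. With S = 0.5, g = 42 and p = 1: 0.5^(407/365) − 0.5 = 0.462 − 0.5 = −3.8 points.

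*Lost PFS time.* If one early death drops out of 14, k/14 becomes k/13. For k = 1: 7.7% − 7.1% = 0.5 points. For k = 7: 53.8% − 50.0% = 3.8 points.

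*Censoring date.* A patient censored at DT_EOS beyond month 12 counts fully as progression-free at 1 year. Censored instead at last scan c, the patient contributes about S(12)/S(c). The difference is (1 − S(12)/S(c))/14. Under exponential PFS:
- Median 3 months, c = week 6: S(12) = 0.0625, S(c) = 0.727, giving (1 − 0.086)/14 = 6.5 points.
- Median 6 months, c = week 18: S(12) = 0.25, S(c) = 0.620, giving (1 − 0.403)/14 = 4.3 points.

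**Step 3. Can unscanned time on study arise?** Yes. A patient who starts new therapy without progression leaves the 12-weekly follow-up and moves to the 6-monthly one, still on study. Protocol 4.4 and 4.9 set no imaging schedule for that period.

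**The case against.** The strongest reply concerns DT_EOS. It sits on the same form as REA_STUD and DT_DEATH, and Protocol 4.4 says "Study discontinuation occurs when an enrolled patient ceases to participate in the study". When the reason is death, the natural end-of-study date is the death date, and the PFS dating error vanishes. That reading is fair, and the documents do not exclude it. They do not state it either, and nothing comparable supports DT_LFUP, whose label points to a visit or contact date.

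Second, the programs are specification sketches rather than final code. They begin with a completeness check, and Protocol 11.2.5 requires a validated checklist before data lock. A programmer might well catch patient D. That makes the loss avoidable, but no action is written for it.

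Third, last-scan censoring is a choice, and no written rule is broken by using DT_EOS. This stands: the criticism is that the choice is neither stated in words nor justified.

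Two stronger readings should be resisted. A reader might infer that the SAP has no PFS censoring rule at all. It has one in code: DT_EOS with IND_PFS=0. A reader might also infer that any blank PRO_LAS destroys the PFS time. It does so only when DT_PROG and DT_FPROG are blank as well, as patient E shows.

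**Conclusion.** Wrong as written. The programs return the defined PFS and OS only if certain fields happen to hold the death date, if PRO_LAS is completed for patients with no recorded progression, and if the forms agree. The dating of deaths and the blank-field branch are the firm points. The unread STATUSP is a robustness gap that matters only with conflicting forms. The censoring date is an undocumented choice that can count unscanned time as progression-free.

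The size is unknown and may be zero. All figures above rest on assumed dates, exponential survival and assumed rates. A reader might infer that the reported 1-year PFS or OS will be inflated; the documents do not support that. The OS dating error can run either way, and the censoring effect is zero if no such patient occurs, if a later progression is recorded, or if DT_EOS is the patient's own stop date.

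The consequences are limited to descriptive secondary endpoints. The one-response rule (Protocol 9.1.1, expansion cohorts) and the choice of RP2D (Protocol 3.2) use neither endpoint.

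**What to change.** Amend SAP 3.2.4 as follows.

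1. In both programs, date every death recorded by STATUSP or REA_STUD at DT_DEATH. Because DT_DEATH is on the end-of-study form, it may be blank for a death known only from follow-up; require a query or state a fallback date.
2. Define the PFS event as the earliest of DT_PROG, DT_FPROG and death.
3. Send a blank PRO_LAS to the no-progression branch or to a query, never to the event branch.
4. Otherwise censor PFS at the last evaluable tumour assessment. First confirm that DT_MEASC, or another CRF field, covers scans after treatment; if it holds only on-treatment scans, long-term non-progressors would be censored too early.
5. Censor OS survivors at the date last known alive.
6. Define DT_EOS and DT_LFUP for a patient who has died, and write the censoring rules in words.

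Censoring at new antitumour therapy could be added as a sensitivity analysis if that date is collected.

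The cost is a few lines of specification. DT_DEATH, STATUSP, REA_STUD and DT_MEASC are already listed in the SAP. Post-treatment scan dates and new-therapy dates need a CRF check before anyone relies on them.
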